**Table S-1: Study Objectives and Endpoints**

Objectives	Endpoints
Primary	

 
• To evaluate the efficacy of ETX-018810 for the treatment of lumbosacral radicular pain (LSRP)
 
	
 
• Change from baseline to Week 4 in the weekly average of the daily pain score on the 11-point Pain Intensity Numerical Rating Scale (PI-NRS)
 

Secondary	

 
• To evaluate the efficacy of ETX-018810 on additional pain measures and assessments of disability
 
	
Secondary efficacy endpoints in pain:
 
 
• Response rate, defined as a <math>\geq 50\%</math> reduction from baseline to Weeks 1, 2, 3, and 4 in the weekly average of the daily pain score
 
• Response rate, defined as a <math>\geq 30\%</math> reduction from baseline to Weeks 1, 2, 3, and 4 in the weekly average of the daily pain score
 
• Change in the weekly average of the daily pain score from baseline to Weeks 1, 2, and 3
 
• Change from baseline to Week 4 for worst pain
 
 
Secondary efficacy endpoints:
 
 
• Response rate on the Patient Global Impression of Change (PGIC) scale at Week 4, defined as the proportion of subjects who are “much improved” or “very much improved”
 
• Response rate on the Clinical Global Impression of Change (CGIC) scale at Week 4, defined as the proportion of subjects who are “much improved” or “very much improved”
 
• Change in the weekly average of the daily sleep score on the Daily Sleep Interference Scale (DSIS) from baseline to Weeks 1, 2, 3, and 4
 
• Change from baseline to Week 4 in the Brief Pain Inventory (BPI)
 
• Change from baseline to Week 4 in the Roland-Morris Disability Questionnaire
 
• Amount of rescue mediation used (dosage/day)
 

 
• To investigate the safety and tolerability of ETX-018810 in subjects with LSRP
 
	
 
• Nature, frequency, and severity of nonserious treatment-emergent adverse events (TEAEs) and serious adverse events (SAEs)
 
• Frequency of discontinuations due to TEAEs or death
 

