7 days meets the study-specified threshold, who completed the PI-NRS and DSIS in the eDiary on at least 5 of the 7 days before the baseline/Day 1 visit, and who continue to meet all other study eligibility criteria will be enrolled in the study. The baseline assessment of eligibility will be made using a computerized screening algorithm on the basis of the information that is recorded in the eDiary. The investigator, site team, and study monitors will be blinded to the screening algorithm. The investigator/site staff will be informed as to whether the algorithm classifies the subject as eligible or ineligible and will inform the subject if he/she is eligible to continue in the study. Subject will be randomized to receive double-blind treatment with ETX-018810 1000 mg or placebo twice daily (BID) for 4 weeks at the baseline/Day 1 visit. Subjects will be trained on scoring of their pain intensity at the baseline visit.

Subjects will continue to use the eDiary to record their LSRP pain score, as defined above, over the last 24 hours on the PI-NRS (once daily in the evening when they take their second daily dose of investigational product), their sleep interference as a result of their LSRP on the DSIS (once daily in the morning when they take their first daily dose of investigational product), and rescue medication use (once daily in the evening when they take their second daily dose of investigational product) throughout the 4-week double-blind treatment period. Subjects will be allowed to take acetaminophen at a dose of up to 2600 mg/day for up to 3 consecutive days, but for no more than a total of 7 days, for non-LSRP-related pain (headache, toothache, etc) or for breakthrough pain due to LSRP.

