**Number of Subjects:**

Approximately 203 subjects will be screened to achieve a minimum of 122 randomized subjects (61 per treatment group). Subjects for whom diary data is unavailable due to technical issues may be replaced.

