**Treatment Groups and Duration:**

Each subject will participate in the study for approximately 9 weeks, including a screening period of up to 4 weeks; a 4-week, double-blind treatment period; and a 1-week posttreatment follow-up period. Subjects will be randomized in a 1:1 ratio to receive 1000 mg of ETX-018810 or placebo BID for 4 weeks.

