**Statistical Analysis Plan:**

The analysis populations were defined as:

- Safety Population - All subjects who received at least 1 dose of study treatment.
- Intent-to-treat (ITT) Population - All randomized subjects who received at least 1 dose of study treatment.
- Modified intent-to-treat (mITT) Population - All subjects in the ITT population who had at least 4 postbaseline measurements for the Pain Intensity Numeric Rating Scale (PI-NRS) in the eDiary.

The mITT population was used for the primary analysis of the primary efficacy endpoint and for all other eDiary efficacy endpoints; the ITT population was used for the analyses of the secondary efficacy endpoints. The safety population was used for the safety analyses.

Continuous data were summarized using descriptive statistics (e.g., mean, standard deviation), and categorical data were summarized using counts and percentages.

For the PI-NRS and DSIS (for which scores were completed daily in the eDiary), the weekly average was the mean of the non-missing scores for the 7-day period; the weekly average was calculated if at least one score was recorded for the week.

The treatment comparison for the change from baseline at Week 4 was estimated using a Mixed Model Repeated Measures (MMRM), which included the baseline score as a covariate; treatment group, visit (week), and the treatment-by-visit (week) as fixed effects; and a repeated structure that acknowledged the visits within a subject using an unstructured covariance structure. The Kenward-Rogers (1997) approximation was used to estimate the denominator degrees of freedom. The estimate, standard error, 90% CI, and associated p-value (2-sided) were presented.

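### Does the Week 4 MMRM need a baseline-by-week term, given that it applies one baseline slope to all four weeks?

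*Combined protocol and SAP*

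**What the plan says.** Table S-1 gives the primary endpoint as "Change from baseline to Week 4 in the weekly average of the daily pain score" on the PI-NRS. The Statistical Analysis Plan section of the synopsis estimates the treatment comparison with an MMRM "which included the baseline score as a covariate; treatment group, visit (week), and the treatment-by-visit (week) as fixed effects", with "a repeated structure that acknowledged the visits within a subject using an unstructured covariance structure" and Kenward-Roger degrees of freedom. No baseline-by-week interaction is listed.

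The primary analysis set is mITT: treated, randomized subjects "who had at least 4 postbaseline measurements for the Pain Intensity Numeric Rating Scale (PI-NRS) in the eDiary". A weekly average needs only one score in the week. Number of Subjects sets "a minimum of 122 randomized subjects (61 per treatment group"), and Treatment Groups and Duration gives 1:1 allocation. The output is described in the past tense: "The estimate, standard error, 90% CI, and associated p-value (2-sided) were presented".

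Only the synopsis is available. It states no baseline slope, weekly SD, between-week correlation, baseline SD, dropout rate, power or alpha.

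**The concern.** The model lets everything vary by week except the influence of baseline. In a pain trial the dependence on baseline may well weaken as weeks pass. If it does, the fitted common slope is a weighted average of the weekly slopes, with weights set by the residual covariance and the pattern of missing weeks. Week 4 need not weigh much in it. Subjects with diary data only in Week 1 can meet the mITT rule and add to the early weeks' weight.

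The Week 4 contrast would then be adjusted with a slope that belongs partly to other weeks, and some of the precision that the covariate should bring would be lost. The extra term is three parameters fitted to data already collected, so leaving it out can look like an oversight.

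**Working it through.** **The plan's own figure.** 2 × 61 = 122 is consistent. The inputs behind 122 are not in the available text, so the sample size cannot be rebuilt, and the point does not depend on it.

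**1. Validity.** With complete data and a treatment effect for each week, both models estimate the Week 4 effect as (difference in Week 4 means) − slope × (difference in baseline means). The stated model uses the common slope bc; the interaction model uses the Week 4 slope b4. Randomization makes the expected baseline difference zero, so the term (b4 − bc) × (baseline difference) averages to zero and the estimate is unbiased for any bc. The misfit goes into the unstructured covariance, V = S + SD_b²(b − bc)(b − bc)′, where S is the residual covariance across weeks, b the vector of weekly slopes and SD_b the baseline SD. The standard error therefore reflects it. Only precision is left to discuss.

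**2. Cost of the extra term.** Estimating a separate Week 4 slope adds 1/(N − 4) = 1/118 = 0.85% to the Week 4 variance, compared with a known slope. Against a correct common slope the net cost is (1 − vc/s44)/118, with vc = 1/(1′S⁻¹1) and s44 the Week 4 residual variance. For flat SDs and exchangeable correlation 0.5, vc/s44 = 0.625, and 0.375/118 = 0.32%. Simulation at 122 subjects over five assumed correlation structures gives 0.1 to 0.5%.

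**3. Possible gain.** In large samples the variance lost by the common slope is (b4 − bc)² × SD_b²/s44. Slopes below are for the pain score; for the change score each is lower by 1, so the gaps are the same. All inputs are assumptions: Week 4 residual SD 1.8 (s44 = 3.24); weekly SDs flat at 1.8 or growing 1.2, 1.4, 1.6, 1.8; SD_b 0.9 to 1.5.

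- Fall of 0.35 (0.85, 0.70, 0.60, 0.50), flat SDs, exchangeable 0.5, SD_b 0.9: equal weights give bc = 0.6625, gap 0.1625. Loss 0.1625² × 0.81/3.24 = 0.66%. Less the 0.32% cost, about 0.3%; simulation puts the low end at 0.4%.
- Same fall, growing SDs, exchangeable 0.7, SD_b 1.5: bc = 0.849, gap 0.349. Loss 0.349² × 2.25/3.24 = 8.5%; net 8.0%. This is the largest saving for a fall.
- Linear fall of 0.1, flat SDs, exchangeable 0.5, SD_b 0.9: gap 0.05. Loss 0.05² × 0.81/3.24 = 0.06%, less than the 0.32% cost, so the extra term makes the Week 4 estimate slightly worse.

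**4. Net change in Week 4 variance from adding the term** (122 subjects, complete data, simulated; positive means a saving):

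| Slope path | Flat SDs | Growing SDs |
|---|---|---|
| Equal | −0.3 to −0.1% | −0.5% |
| Fall 0.1 | −0.2 to 0.0% | −0.4 to +0.3% |
| Fall 0.2 | −0.1 to +0.9% | +0.1 to +2.5% |
| Fall 0.35 | +0.4 to +2.7% | +1.3 to +8.0% |
| Rise 0.35 | +0.5 to +3.4% | +1.3 to +8.8% |

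The break-even linear fall is 0.10 to 0.225, depending on the covariance and SD_b.

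**5. What this means for power.** With 80% power assumed for the interaction model and f the variance ratio, power = Φ((z + 0.842)/√f − z). For f = 1.02 this is 79.3% at two-sided alpha 0.10 (z = 1.645) and 79.2% at 0.05 (z = 1.960). For f = 1.085 it is 77.1% and 76.7%.

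**The case for a change.** The best case for changing the model is that the bet is lopsided. The cost averages half a percent of variance or less, while the saving could reach several percent. The mechanism is real. With growing SDs, Week 1 carries weight 0.58 to 0.97 in the common slope in all five structures, and Week 4 at most 0.16. Even with flat SDs, correlation 0.5 between Week 1 and later weeks and 0.8 among later weeks gives Week 1 weight 0.42 and Week 4 0.19. With exchangeable 0.7 and an assumed 15% monotone dropout the weights are 0.30 and 0.22.

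That arithmetic stands, and a sponsor with evidence of drift could reasonably choose the interaction model. But uneven weights do no harm unless the slopes differ, and nothing available shows that they do.

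The upper figures need a large drift, SDs growing by half (1.2 to 1.8), a favourable correlation and SD_b 1.5, all at once. Entry requires that the pain average over the final "7 days meets the study-specified threshold", which narrows the baseline spread by an unknown amount. At SD_b 0.9 the 0.35 fall saves only 0.4 to 0.8% (flat) or 1.3 to 2.6% (growing).

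The low cost is also an average over randomizations: with a chance baseline imbalance near the 5% level the net cost is about 0.2 to 2.2%. Finally, the analysis section is in the past tense while the design sections use the future. If the analysis has been done, only a post hoc sensitivity analysis remains, and that cannot sharpen the primary estimate.

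**Conclusion.** The concern does not hold. The stated MMRM is coherent and, with complete data under randomization, gives an unbiased Week 4 contrast and a valid test. A baseline-by-week term is an alternative whose effect on Week 4 variance runs, over the assumed falls and equal slopes, from a loss of 0.5% to a saving of 8.0% (8.8% for a rise of 0.35). The available text does not settle even the sign. Nothing in the plan has to change.

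This rests on assumed SDs, correlations and slopes, on 122 subjects contributing, and on the synopsis alone; a fuller statistical section might specify more terms. The mITT size at Week 4 is not given: the gross cost would be 1/94 = 1.06% at 98 subjects. With equal slopes and 15% dropout a simulated fit gave a variance ratio of 1.005 (interaction over common slope). Unequal slopes combined with dropout were not simulated, so neither the gain nor any small bias in that case has been quantified.

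### Does a 90% CI beside a two-sided p-value, with no stated significance level, make the primary Week 4 result contradictory?

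*Combined protocol and SAP*

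**What the plan says.** Table S-1 makes the change from baseline to Week 4 in weekly average PI-NRS pain the primary endpoint. Under Statistical Analysis Plan, the synopsis estimates the Week 4 treatment comparison with an MMRM and closes the description with: "The estimate, standard error, 90% CI, and associated p-value (2-sided) were presented". On the analysis set it says: "The mITT population was used for the primary analysis of the primary efficacy endpoint and for all other eDiary efficacy endpoints". For the t reference distribution, a Kenward-Roger "approximation was used to estimate the denominator degrees of freedom".

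Number of Subjects gives a minimum of 122 randomized, 61 per group, from about 203 screened. It gives no significance level, power, effect size or standard deviation. Overall Design calls the trial Phase 2. The supplied synopsis states no significance level, no one-sided hypothesis and no success criterion, and it does not say why 90% was chosen.

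**The concern.** Most readers pair a two-sided p-value with a 95% interval and judge both at 0.05. Here the interval is 90%, which is the counterpart of a two-sided 0.10 test or a one-sided 0.05 test. If p fell between 0.05 and 0.10, one reader could call the trial positive because the interval excludes zero, and another could call it negative because p exceeds 0.05. With no level written down, the choice could in principle be made after the result is known. If exclusion of zero by the interval were the criterion, the two-sided false-positive rate would be 10%. Because this is the primary comparison, the trial's efficacy conclusion would be at stake.

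**Working it through.** **Inputs.** From the synopsis: 61 per group, 1:1 allocation, 90% CI, two-sided p-value, Kenward-Roger degrees of freedom. Assumed: about 120 degrees of freedom for the between-group contrast (80 checked as a lower value), standardized effects from 0 to 0.5, and an SD of 1.8 to 2.5 PI-NRS points. The documents give no effect size or SD.

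**The plan's own figures.** 2 × 61 = 122, and 122/203 = 60.1%, so about 40% screen failure is implied. The 122 cannot be derived from a power calculation, because none of its inputs is given. It does not reveal the intended level either. With (z for alpha + z for power) × √(2/61), 80% power needs a standardized effect of 0.507 at two-sided 0.05 and 0.450 at two-sided 0.10. Either could have been the design target.

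**Do the interval and the p-value agree?** Both come from the same contrast, with t = estimate/SE. The 90% interval is estimate ± t(0.95) × SE, so it excludes zero when |t| > t(0.95), which is the same event as two-sided p < 0.10. There is no internal conflict.

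**Where a reader using 0.05 would see a mismatch.**

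| df | 90% multiplier | 95% multiplier | ratio |
|---|---|---|---|
| 80 | 1.664 | 1.990 | 1.196 |
| 120 | 1.658 | 1.980 | 1.194 |

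Example at 120 df: t = 1.80 gives p = 0.074. The lower 90% limit is 1.80 − 1.658 = 0.14 SE above zero. The lower 95% limit would be 1.980 − 1.80 = 0.18 SE below zero.

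**How often.** Normal approximation with 61 per group: P(|Z| > 1.645) − P(|Z| > 1.960), where Z has mean d/√(2/61).

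| assumed d | excludes zero at 90% | p < 0.05 | difference |
|---|---|---|---|
| 0 | 10.0% | 5.0% | 5.0% |
| 0.2 | 29.75% | 19.72% | 10.0% |
| 0.3 | 50.52% | 38.10% | 12.4% |
| 0.4 | 71.38% | 59.84% | 11.5% |
| 0.5 | 86.79% | 78.85% | 7.9% |

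**On the pain scale.** With SE = SD × √(2/61) and about 119 df, an SD of 2.0 gives SE 0.362 and half-widths of 1.658 × 0.362 = 0.60 and 1.980 × 0.362 = 0.72 points. The band is 0.54 to 0.65 at SD 1.8 and 0.75 to 0.90 at SD 2.5. These figures are only illustrative: the SDs are assumed, and the formula ignores the baseline adjustment, the repeated measures and any loss from the randomized set to the mITT set.

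**What a change to 95% would alter.** The estimate, SE and p-value stay the same. The displayed interval widens by the ratio above, about 19%. A reader can already compute estimate ± 1.98 × SE, or multiply the reported half-width by 1.19.

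**The case for a change.** The strongest case for a change is that a primary analysis should carry its decision level. The sample size does not show whether 0.05 or 0.10 was meant. At modest true effects of 0.2 to 0.4 SD, about one trial in eight to ten would land where the two common readings diverge. A 90% interval is legitimate in Phase 2, but then the level should be declared, and declaring it costs one sentence.

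Part of this stands. The supplied synopsis states no level and gives no reason for 90%, and someone who assumes 0.05 could misread a p-value between 0.05 and 0.10. The arithmetic is also correct.

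The rest does not carry over to a defect in the analysis. The divergence needs a 0.05 threshold that the reader supplies. The synopsis says these quantities are presented and nowhere makes exclusion of zero a rule for success, so the 10% error rate is not a property of the plan as written. Two-sided 0.10 or one-sided 0.05 is a possible intention in a Phase 2 study, and the argument for a change accepts either level once it is declared. The absence itself is shown only for a synopsis from which some material was removed before review; it is weaker evidence than silence in a full SAP. Finally, the statistical text is in the past tense. If it was written after the analysis, a level declared now would be post hoc. The useful step would then be to report whichever level was fixed before unblinding, which leaves the analysis as it is.

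**Conclusion.** No change to the plan is needed. The 90% interval and the two-sided p-value are two views of one MMRM contrast and agree at the 0.10 level. Followed as written, the plan yields a valid estimate, standard error and two-sided p-value, and the p-value can be judged at any threshold. Moving to 95% would widen the displayed interval by about 19% and change nothing else.

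The possible misreading is confined to 0.05 ≤ p < 0.10. Its probability is 5.0% under no effect and 7.9% to 12.4% at assumed standardized effects of 0.2 to 0.5, with 61 per group and a normal approximation. Those percentages describe how often a reader who assumes 0.05 would see the interval and the test part ways; they do not show an inflated error rate.

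This conclusion rests on the supplied synopsis alone. If a fuller plan made exclusion of zero by the 90% interval the success rule while also naming two-sided 0.05 as the test level, there would be a real conflict. Nothing supplied says so.
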